2.3 Exploratory Objectives

To determine:

- Undetectable PSA at 11 months (cycle 11) (irrespective of testosterone level)
- Time to PSA progression defined as the time to PSA increase that is $\geq 25\%$ and $\geq 2\text{ng/mL}$ above the nadir, and which is confirmed by a second value > 3 weeks later
- Change in PSA doubling time at 24 months relative to PSA doubling time from the first dose of study drug (using the last 3 values from each time point)
- Comparison of Patient Reported Outcome (PRO) assessments of toxicity (PRO-CTCAE) to clinician reported toxicity assessments (CTCAE v.5.0)
- Changes in immune biomarkers with treatment. Peripheral blood mononuclear cells (PBMCs) will be collected that can later be analyzed for the immunomodulatory effects of the regimen by measuring for example, discrete T-cell populations. Archival tissue will also be analyzed for immune-related genes that may associate with response.

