5. TREATMENT/INTERVENTION PLAN

This is a phase II, single arm, multi-center trial that will evaluate the combination of olaparib 300mg twice daily (600mg total daily dose) with durvalumab 1500mg IV monthly in biochemically recurrent castration sensitive prostate cancer. The trial will be conducted at sites who are members of the PCCTC Network.

As seen in the trial design (Figure 2), subjects will be treated concurrently with olaparib + durvalumab continuously for 24 months. After the first 4 months, if a subject fails to achieve an undetectable PSA with the combination of olaparib and durvalumab, ADT will be added for 6 months (starting at Cycle 5) while continuing treatment with olaparib and durvalumab. For subjects who have an undetectable PSA [PSA of <0.05 or PSA <0.10] for institutions where this is the lower limit of detection] after the first 4 months of treatment, they will continue on the combination of olaparib + durvalumab continuously for 24 months (without ADT). As long as it is believed that subjects are clinically benefiting, they will remain on treatment for up to 24 months with olaparib and durvalumab. For example, a subject with a PSA reduction that does not achieve an undetectable PSA would be allowed to remain on study for the duration of the trial. Subjects who meet progression criteria while on active therapy would come off of trial. If subjects respond and later progress in the one-year follow-up period (beyond 24 months), they will be allowed to be re-induced with the combination.

Figure 2. Study schema for olaparib and durvalumab in subjects with castration-sensitive prostate cancer (biochemical recurrence) harboring DNA damage repair mutations

DDR deleterious mutations (somatic or germline) will include BRCA1 (breast cancer susceptibility gene), BRCA2, ATM (ataxia telangiectasia mutated serine/threonine kinase), CHEK2, FANCA, RAD51C, RAD51D, PALB2, BRIP1, BARD1, and CDK12. Mutations may be truncating, splice site mutations, missense or homozygous deletions. Subjects will be allowed on trial using local testing, previously obtained genomic testing from a validated lab (e.g., expedited germline testing from Color), or via archival or fresh tissue.

The following assessments and procedures will occur during the study. A schedule of assessments is provided in Appendix B.

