5.3 Follow-up (Every 12 weeks)

Subjects will be followed per the schedule in Appendix B. Subjects withdrawn from the study because of AEs will be followed until the adverse event has either resolved or stabilized. Reasons for premature withdrawal should be determined and noted.

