5.7 Removing Subjects from the Protocol

In the absence of treatment delays because of adverse events, treatment will continue for 24 cycles or until one of the following criteria applies:

- Withdrawal by subject: subject decides to withdraw from the study
- Progressive disease. PSA progression during the treatment period is defined as a rising PSA confirmed on repeat measurement at least two weeks later and at a least 25% rise and 2 ng/mL above nadir or baseline, whichever is lower. The assessment for PSA progression that may lead to discontinuation while on treatment will not begin prior to Cycle 6 as ADT would not start until Cycle 5. PSA progression during the follow up period defined as PSA > 0.2 ng/mL confirmed by repeat measurement at least 2 weeks later.
- symptomatic disease progression at any time
- objective clinical disease progression
- Intercurrent illness that prevents further administration of treatment, including bone marrow findings consistent with myelodysplastic syndrome (MDS)/acute myeloid leukemia (AML)
- Adverse event: unacceptable adverse event(s) that may or may not be directly related to treatment but that, in the judgment of the treating physician, makes it dangerous for the subject to be retreated
- Physician decision: general or specific changes in the subject's condition that render the subject unacceptable for further treatment, in the judgment of the investigator

Because an excessive rate of withdrawals can render the study uninterpretable, unnecessary withdrawal of subjects should be avoided. When a subject discontinues treatment early, the investigator should make every effort to contact the subject and to perform a final evaluation. The reason(s) for withdrawal should be recorded.

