6.5 Treatment Delay

Subjects receiving durvalumab or olaparib who require therapy delay of more than 8 weeks due to toxicity will be removed from treatment but will be followed according to the schedule of assessments. If toxicity is attributed to a single agent, upon discussion with the Sponsor Principal Investigator, subjects may continue the other drug.

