10.5 Statistical Procedures and Analysis

Summary statistics include the number of observations, mean, standard deviation, median, minimum, and maximum values.

Statistical methods for the analyses

An exact binomial test will be used to evaluate the efficacy of the 24 months undetectable PSA endpoint. In addition, the proportion of subjects that attain an undetectable PSA at (1) 5 months, (2) 11 months, and (3) 24 months will be computed along with their attendant 95% confidence intervals. The probability of PSA progression over time will be estimated using the cumulative incidence function.

A paired t-test will be used to compare the PSA doubling time at 24 months to the PSA doubling time at study entry.

Kendall's tau with longitudinal data will be used to compare patient recorded toxicities to physician recorded toxicities over time.

The immunologic profile of patients over time will be described using nonparametric kernel smoothing.

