- q. A blood or saliva sample will be collected during screening as matched normal for sequencing for patients completing prospective Next Generation Sequencing using assays that require a matched normal sample.
- r. Subjects will be treated concurrently with olaparib + durvalumab continuously for 24 months. Durvalumab will be administered on Day 1 of each cycle (± 3). After the first 4 months, if a subject fails to achieve an undetectable PSA [PSA of <0.05 (or PSA <0.10 for institutions where this is the lower limit of detection) with the combination of olaparib and durvalumab, ADT will be added for 6 months (starting at Cycle 5) while continuing treatment with olaparib and durvalumab (see section 6.3 for additional details regarding ADT). For subjects who have an undetectable PSA after the first 4 months of treatment, they will continue on the combination of olaparib + durvalumab continuously for 24 months (without ADT). As long as it is believed that subjects are clinically benefiting, they will remain on treatment for up to 24 months with olaparib and durvalumab. For example, a subject with a PSA reduction that does not achieve an undetectable PSA would be allowed to remain on study for the duration of the trial. Subjects who meet progression criteria while on active therapy would come off of trial.
- s. Subjects who have an undetectable PSA after completion of protocol therapy will be followed every 12 weeks. PSA, CMP, CBC, and TFTs should be performed. A physical exam will be performed. Subjects who respond and later progress in the first year following the 24 month treatment phase will be allowed to re-induce with the combination and will restart their calendar with C1D1 if they continue to meet all clinical eligibility criteria are met. PCCTC must review the confirmation of eligibility prior to re-inducing treatment.

APPENDIX C. ACTIONS REQUIRED IN CASES OF COMBINED INCREASE OF AMINOTRANSFERASE AND TOTAL BILIRUBIN – HY'S LAW

Introduction

This Appendix describes the process to be followed in order to identify and appropriately report cases of Hy's Law. It is not intended to be a comprehensive guide to the management of elevated liver biochemistries. Specific guidance on the managing liver abnormalities can be found in Appendix H and Appendix I of the protocol.

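### Post-treatment PSA is scheduled only for men whose PSA is undetectable, so a PSA-progression curve carried past month 24 would be informatively censored

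*Combined protocol and SAP*

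**What the plan says.** Section 5.3 sets no PSA condition of its own and defers to the calendar: "Subjects will be followed per the schedule in Appendix B". In Appendix B the follow-up column carries footnote s, which reads: "Subjects who have an undetectable PSA after completion of protocol therapy will be followed every 12 weeks". No other passage schedules PSA after treatment.

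Two groups can leave treatment without having progressed and without an undetectable PSA. Section 5 gives the example that "a subject with a PSA reduction that does not achieve an undetectable PSA would be allowed to remain on study for the duration". Section 6.5 says that men whose therapy is delayed by more than 8 weeks for toxicity "will be removed from treatment but will be followed according to the schedule of assessments", with no condition on PSA. Men who do progress on treatment are handled separately: "Subjects who meet progression criteria while on active therapy would come off of trial".

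Section 2.3 lists time to PSA progression as an exploratory objective, and Section 10.1.4 lists PSA PFS. The analysis is one sentence in Section 10.5: "The probability of PSA progression over time will be estimated using the cumulative incidence function". It states no horizon, censoring rule or competing event.

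Progression is defined in two ways. Section 2.3 requires a rise of at least 25% and at least 2 ng/mL "above the nadir, and which is confirmed by a second value > 3 weeks later". Section 5.7 has a different rule after treatment: "PSA progression during the follow up period defined as PSA > 0.2 ng/mL confirmed by repeat measurement at least 2 weeks later".

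**The concern.** Entry into follow-up depends on PSA at the end of treatment, and PSA also defines the event. A cumulative incidence estimate treats men censored at a given time as having the same future risk as those still observed. Here the men who drop out of observation at the end of treatment would be those with measurable PSA, and the men who stay would be those with none. The first group can be expected to progress sooner.

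What is at stake is the trial's description of durability. Section 1.3.2 hypothesises durable responses, and Section 1.3.1 says endpoints akin to PFS will inform the judgement of efficacy. PSA values not drawn in the year after treatment cannot be recovered later.

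**Working it through.** **1. The plan's own design figure.** Section 10.2 has 32 subjects, success at 8 or more, one-sided size 0.10 at a rate of 0.15, and power above 0.90 at 0.35. Exact binomial: P(X ≥ 8 | 32, 0.15) = 0.0958 and P(X ≥ 8 | 32, 0.35) = 0.918. It reproduces. It does not depend on post-treatment follow-up, because withdrawals before month 24 count as failures.

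**2. Who has a scheduled PSA after treatment.**

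| Status at end of treatment | Event already counted? | Later PSA scheduled? |
|---|---|---|
| Progressed on treatment | Yes | Not needed |
| Completed, undetectable | No | Yes, 12-weekly (footnote s) |
| Completed, detectable, not progressed | No | No |
| Removed for toxicity delay, not progressed | No | Unclear (6.5 against footnote s) |

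Only the third row, and possibly the fourth, is lost.

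**3. Bias if the curve runs to month 36 with one definition.** Let P men have progressed by month 24, u be event-free and undetectable, and d be event-free and detectable, with P + u + d = 32. Let hu and hd be the risks of progression over the following year. Assume all d men are censored at month 24, with no other censoring and no competing event.

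- True incidence = (P + u·hu + d·hd)/32
- Estimated incidence = P/32 + [(u + d)/32]·hu
- Shortfall = d(hd − hu)/32

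Example with P = 12, u = 10, d = 10, hu = 0.2, hd = 0.7: true = (12 + 2 + 7)/32 = 0.656; estimated = 12/32 + (20/32)(0.2) = 0.500; shortfall = 10 × 0.5/32 = 0.156.

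Shortfall in percentage points over the assumed range:

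| d | hd 50%, hu 30% | hd 50%, hu 20% | hd 70%, hu 30% | hd 70%, hu 20% |
|---|---|---|---|---|
| 6 | 3.8 | 5.6 | 7.5 | 9.4 |
| 10 | 6.3 | 9.4 | 12.5 | 15.6 |
| 12 | 7.5 | 11.3 | 15.0 | 18.8 |

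The range is about 4 to 19 points. It is zero if hd = hu, and with d = 2 at 50% against 20% it is 2 × 0.3/32, or 1.9 points. For men who complete treatment there is no bias up to month 24.

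**4. Effect of the two definitions.** From 0.05 ng/mL, reaching 0.2 takes log2(4) = 2 doublings, so it happens within 12 months if the doubling time is 12/2 = 6 months or less. Reaching 2.05 takes log2(41) = 5.36 doublings, which needs 12/5.36 = 2.2 months or less. An undetectable man whose doubling time lies between 2.2 and 6 months is thus an event under 5.7 but not under 2.3.

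A simulation of exponential PSA growth gives the 12-month post-treatment progression below. It assumes half of event-free men are undetectable and none cured.

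| Median doubling time | 2.3 rule: undetectable / all | 5.7 rule: undetectable / all |
|---|---|---|
| 3 months | 26% / 61% | 77% / 88% |
| 6 months | 4% / 43% | 35% / 68% |
| 9 months | 1% / 33% | 15% / 57% |

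Within either rule the undetectable men understate the whole group. If instead undetectable men are scored by 5.7 and the target is the 2.3 endpoint in all men, the comparison is 77% against 61% at 3 months (too high), 35% against 43% at 6 months and 15% against 33% at 9 months (too low).

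**The case against.** The strongest reply is that a month-36 curve is not in the plan. Section 10.5 gives no horizon, Section 8.1.1 plans monthly PSA for the first 24 months, and nowhere is it said that follow-up data enter the curve or that detectable men are censored at end of treatment. Footnote s also covers re-induction of men who respond and later progress, so it can be read as relapse surveillance in responders. This stands as a limit: the bias is conditional on the curve being extended. It does not dispose of the point. Section 2.3 fixes times for its 11-month and 24-month objectives but none for PSA progression, and Section 5.7 defines progression specifically for the follow-up period, so extension is a natural reading.

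A reader might infer that the curve will certainly come out too low. The documents do not support that: the change of definition in Section 5.7 can offset or reverse the direction, as step 4 shows.

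A reader might also infer that the protocol flatly contradicts itself on whether men removed for toxicity are followed. It does not. Footnote s speaks of men who have completed protocol therapy, and Section 6.5 can be read as covering the others. But Section 6.5 points to a schedule whose only follow-up rule is footnote s, so the two are ambiguous together, even for a man who stops early with undetectable PSA.

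Finally, simply widening follow-up would create a new fault. Under the 5.7 rule, a man ending treatment with a stable PSA above 0.2 ng/mL would count as progressed at his first confirmed follow-up value, with no rise at all. That objection is sound and shapes the fix.

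**Conclusion.** The point holds in conditional form. Footnote s selects post-treatment PSA follow-up on PSA status. If the exploratory progression curve is carried past month 24, its censoring is informative, and under one definition applied to everyone it is biased low so long as detectable men progress faster. About 4 to 19 percentage points is an illustration resting on 6 to 12 detectable event-free men and one-year risks of 50–70% against 20–30%. None of these figures comes from the documents. With mixed definitions the sign is not determined.

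Nothing here touches the primary month-24 test or its rule of 8 successes in 32; reading the concern as a threat to the trial's main conclusion would be wrong. It is still worth correcting: the rule is explicit, the repair is small, and the missing values cannot be obtained afterwards.

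**What to change.** Amend footnote s so that every subject who ends protocol therapy without confirmed PSA progression has PSA every 12 weeks through the one-year follow-up. Reconcile it with Section 6.5, so that sites know what applies to men removed for toxicity before completing 24 cycles.

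In Section 10.5, state that the curve uses the Section 2.3 definition throughout, so that a stable detectable PSA above 0.2 ng/mL is not scored as an event. Give the horizon, the censoring rule and the handling of competing events, including re-induction and new therapy. This concerns the analysis only and leaves the Section 5.7 removal criteria as they are.

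The cost is one footnote, a few sentences, and about four extra PSA draws per affected man over the year (52/12 = 4.3).

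If follow-up is not widened, end the curve at month 24 and report post-treatment PSA separately, labelled as conditional on undetectable PSA at end of treatment. That needs no extra draws, but the ambiguity with Section 6.5 must still be settled because it affects the curve before month 24.

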APPENDIX D: MEDICATIONS WITH THE POTENTIAL FOR DRUG-DRUG INTERACTIONS

Olaparib is an investigational drug for which no data on in vivo interactions are currently available. Based on in vitro data and clinical exposure data, olaparib is considered unlikely to cause clinically significant drug interactions through inhibition or induction of cytochrome P450 enzyme activity. In vitro data have, however, also shown that the principal enzyme responsible for the formation of the 3 main metabolites of olaparib is CYP3A4 and consequently, to ensure subject safety, the following potent inhibitors of CYP3A4 must not be used during this study for any subject receiving olaparib.

While this is not an exhaustive list, it covers the known potent inhibitors, which have most often previously been reported to be associated with clinically significant drug interactions.

Prohibited Concomitant Medications while subjects are taking Olaparib:

Agent	Agent
ketoconazole	rifapentine
itraconazole	rifabutin
ritonavir	carbamazepine
indinavir	phenobarbitone
saquinavir	nevirapine
telithromycin	modafinil
clarithromycin	St John's Wort (Hypericum perforatum)
nelfinavir	
phenytoin	
rifampicin	

After enrollment if the use of any potent inducers or inhibitors of CYP3A4 are considered necessary for the subject's safety and welfare, the Sponsor Principal Investigator must contact the AstraZeneca Study Physician. A decision to allow the subject to continue in the study will be made on a case-by-case basis.

If there is no suitable alternative concomitant medication then the dose of olaparib should be reduced for the period of concomitant administration. The dose reduction of olaparib should be recorded in the CRF with the reason documented as concomitant CYP3A inhibitor use.

- Strong CYP3A inhibitors – reduce the dose of olaparib to 100mg BID for the duration of concomitant therapy with the strong inhibitor and for 5 half-lives afterwards.
- Moderate CYP3A inhibitors - reduce the dose of olaparib to 150mg BID for the duration of concomitant therapy with the moderate inhibitor and for 3 half-lives afterwards.
- After the washout of the inhibitor is complete, the olaparib dose can be re-escalated.

Strong or Moderate CYP3A inducers

Strong (e.g., phenobarbital, phenytoin, rifampicin, rifabutin, rifapentine, carbamazepine, nevirapine, enzalutamide and St John's Wort) and moderate CYP3A inducers (e.g. bosentan, efavirenz, modafinil) of CYP3A should not be taken with olaparib.

If the use of any strong or moderate CYP3A inducers are considered necessary for the subject's safety and welfare this could diminish the clinical efficacy of olaparib.

If a subject requires use of a strong or moderate CYP3A inducer or inhibitor then they must be monitored carefully for any change in efficacy of olaparib.

P-gp inhibitors

It is possible that co-administration of P-gp inhibitors (e.g. amiodarone, azithromycin) may increase exposure to olaparib. Caution should therefore be observed.

Effect of olaparib on other drugs

Based on limited *in vitro* data, olaparib may increase the exposure to substrates of CYP3A4, P-gp, OATP1B1, OCT1, OCT2, OAT3, MATE1 and MATE2K.

Based on limited *in vitro* data, olaparib may reduce the exposure to substrates of CYP3A4, CYP1A2, 2B6, 2C9, 2C19 and P-gp.

The efficacy of hormonal contraceptives may be reduced if co administered with olaparib.

Caution should therefore be observed if substrates of these isoenzymes or transporter proteins are co-administered.

Examples of substrates include:

- CYP3A4 – hormonal contraceptive, simvastatin, cisapride, cyclosporine, ergot alkaloids, fentanyl, pimozide, sirolimus, tacrolimus and quetiapine
- CYP1A2 – duloxetine, melatonin
- CYP2B6 – bupropion, efavirenz
- CYP2C9 – warfarin
- CYP2C19 - lansoprazole, omeprazole, S-mephenytoin
- P-gp - simvastatin, pravastatin, digoxin, dabigatran, colchicine
- OATP1B1 - bosentan, glibenclamide, repaglinide, statins and valsartan
- OCT1, MATE1, MATE2K – metformin
- OCT2 - serum creatinine
- OAT3 -furosemide, methotrexate

Natural/Herbal Products

The use of any natural/herbal products or other traditional remedies should be discouraged, but use of these products, as well as use of all vitamins, nutritional supplements, and all other concomitant medications must be recorded in the case report form (CRF).

It is not recommended to consume grapefruit juice while on olaparib therapy.

Vaccines

Live virus and live bacterial vaccines, with the exception of shingles vaccine (live), should not be administered while the subject is receiving study medication until 30 days after the last dose of study therapy.

Anticoagulant Therapy

Subjects who are taking warfarin may participate in this trial; however, it is recommended that international normalized ratio (INR) be monitored carefully at least once per week for the first month, then monthly if the INR is stable. Subcutaneous heparin and low molecular weight heparin are permitted.

Anti-emetics/Anti-diarrheal

If a subject develops nausea, vomiting and / or diarrhea, then these symptoms should be reported as AEs and appropriate treatment of the event given.

Administration of other anti-cancer agents

Subjects must not receive any other concurrent anti-cancer therapy, including investigational agents, while on study treatment. No other chemotherapy, immunotherapy, hormonal therapy or other novel agent is to be permitted while the subject is receiving study medication.

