In vitro, CYP3A4 was shown to be the enzyme primarily responsible for the metabolism of olaparib. Following oral dosing of ^{14}C -olaparib to female patients, unchanged olaparib accounted for the majority of the circulating radioactivity in plasma (70%). It was extensively metabolized with unchanged drug accounting for 15% and 6% of radioactivity in urine and feces, respectively. The majority of the metabolism is attributable to oxidation reactions with a number of the components produced undergoing subsequent glucuronide or sulfate conjugation.

Excretion

A mean (\pm standard deviation) terminal plasma half-life of 11.9 ± 4.8 hours and apparent plasma clearance of 8.6 ± 7.1 L/h were observed after a single 400 mg dose of olaparib.

Following a single dose of ^{14}C -olaparib, 86% of the dosed radioactivity was recovered within a 7-day collection period, 44% via the urine and 42% via the feces. The majority of the material was excreted as metabolites.

Based on preliminary data from a dedicated renal impairment trial, the mean AUC and C_{\max} of olaparib increased by 1.5 and 1.2-fold, respectively, when olaparib was dosed in patients with mild renal impairment ($\text{CLcr} = 50-80$ mL/min; $N=14$) compared to those with normal renal function ($\text{CLcr} > 80$ mL/min; $N=8$). There are no data in patients with $\text{CLcr} < 50$ mL/min or in patients on dialysis.

Drug Interactions

In vitro, olaparib was an inhibitor of CYP3A4 and an inducer of CYP2B6 at higher concentrations than are clinically achieved. Olaparib produced little/no inhibition of other CYP isozymes. *In vitro* studies have shown that olaparib is a substrate of CYP3A4.

Based on the data from a drug-interaction trial ($N=57$), the AUC and C_{\max} of olaparib increased by 2.7- and 1.4-fold, respectively, when olaparib was administered in combination with itraconazole, a strong CYP3A inhibitor. Simulations using physiologically-based pharmacokinetic (PBPK) models suggested that a moderate CYP3A inhibitor (fluconazole) may increase the AUC and C_{\max} of olaparib by 2- and 1.1-fold, respectively.

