Based on the data from a drug-interaction trial ($N=22$), the AUC and C_{\max} of olaparib decreased by 87% and 71%, respectively, when olaparib was administered in combination with rifampicin, a strong CYP3A inducer. Simulations using PBPK models suggested that a moderate CYP3A inducer (efavirenz) may decrease the AUC and C_{\max} of olaparib by 50 - 60% and 20 - 30%, respectively. *In vitro* studies have shown that olaparib is a substrate of P-gp and an inhibitor of BCRP, OATP1B1, OCT1, OCT2, OAT3, MATE1 and MATE2K. The clinical relevance of these findings is unknown.

For more information refer to the current version of the olaparib IB.

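### Appendix D lists nine CYP3A inducers under a lead-in that calls them potent inhibitors, so the scope of its olaparib dose-reduction sentence is unclear and the page does not agree with section 6.2.

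*Combined protocol and SAP*

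**What the plan says.** Appendix D opens by stating that no in vivo interaction data are available for olaparib. It then introduces the table of prohibited drugs with the words "the following potent inhibitors of CYP3A4 must not be used during this study for any subject receiving olaparib", and describes the table as covering the known potent inhibitors. The table holds 17 agents.

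The next paragraph deals with exceptions and takes in both classes: "After enrollment if the use of any potent inducers or inhibitors of CYP3A4 are considered necessary". It requires contact with the drug supplier's study physician and a case-by-case decision on whether the subject continues. Directly after it comes the dosing sentence: "If there is no suitable alternative concomitant medication then the dose of olaparib should be reduced for the period of concomitant administration". That sentence names no class. The text after it does: the CRF reason is inhibitor use, two bullets give dose levels for strong and moderate inhibitors (100 mg and 150 mg BID), and a third covers re-escalation after the inhibitor has washed out.

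Inducers then have their own heading. The agents that should not be taken with olaparib are given as "Strong (e.g., phenobarbital, phenytoin, rifampicin, rifabutin, rifapentine, carbamazepine, nevirapine, enzalutamide and St John's Wort) and moderate CYP3A inducers (e.g. bosentan, efavirenz, modafinil". If an inducer is judged necessary, the text warns of lost efficacy and gives no dose action. A last sentence covers subjects on a strong or moderate inducer or inhibitor: "then they must be monitored carefully for any change in efficacy of olaparib".

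Section 6.2 reports that olaparib AUC and Cmax "decreased by 87% and 71%, respectively, when olaparib was administered in combination with rifampicin" (trial with N=22) and "increased by 2.7- and 1.4-fold, respectively, when olaparib was administered in combination with itraconazole" (trial with N=57). Simulations in the same section give AUC down 50-60% with a moderate inducer (efavirenz) and up 2-fold with a moderate inhibitor (fluconazole).

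**The concern.** Inducers and inhibitors move olaparib exposure in opposite directions, so a page that tells sites how to act on an interaction has to say which class each drug belongs to and which class each instruction covers. Appendix D blurs both. A site that trusts the lead-in takes rifampicin or phenytoin to be an inhibitor, and the words in the later text that limit the reduction to inhibitors then no longer exclude those drugs. The monitoring sentence does not separate the classes either. What is at stake is consistent handling of the occasional man who needs one of these drugs during treatment, and a safety appendix that agrees with the protocol's own pharmacology section.

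**Working it through.** The documents' figures here are reported results with no underlying data, so they can be cited but not recomputed. The check is a count, a comparison of passages and one simple scaling.

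**1. Class of each listed agent.** The Appendix D table was matched to the inducer list in the same appendix and to criterion 3.2.8 (taking phenobarbitone as phenobarbital).

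- Named as strong inducers in both places: phenytoin, rifampicin, rifapentine, rifabutin, carbamazepine, phenobarbitone, nevirapine, St John's Wort (8).
- Named as a moderate inducer in both places: modafinil (1).
- Not named as inducers: ketoconazole, itraconazole, ritonavir, indinavir, saquinavir, telithromycin, clarithromycin, nelfinavir (8).

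8 + 1 + 8 = 17, so 9 of the 17 agents carry the wrong class label by the protocol's own classification.

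**2. Scope of the dose-reduction sentence.**

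| Text in Appendix D | Class named |
|---|---|
| Lead-in to the table | inhibitors (but 9 of 17 entries are inducers) |
| Exception and case-by-case review | inducers or inhibitors |
| Dose-reduction sentence | none |
| CRF reason | inhibitor |
| Two dose bullets and the re-escalation bullet | inhibitor |
| Inducer heading and paragraph | inducer, with no dose action |

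Read as a whole, the text leans towards inhibitors only. It never says so in the operative sentence, and the word on which the narrower reading depends is the one that the lead-in misapplies.

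**3. Direction of effect in section 6.2.** AUC relative to the same olaparib dose alone:

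- rifampicin: 1 - 0.87 = 0.13
- moderate inducer (simulated): 1 - 0.60 to 1 - 0.50 = 0.40 to 0.50
- itraconazole: 2.7
- moderate inhibitor (simulated): 2

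Scaling by dose/300 from the 300 mg BID starting dose gives 2.7 x 100/300 = 0.90 for the strong-inhibitor bullet and 2 x 150/300 = 1.00 for the moderate one. This assumes that AUC is proportional to dose. Section 6.2 says that AUC rises less than proportionally over 100-400 mg, so the true values would be somewhat higher. The scaling does not show that those levels are right. It shows only that the bullets offset a rise in exposure, whereas the nine listed inducers belong to the class for which 6.2 reports a fall.

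**4. Monitoring.** The one interaction-specific monitoring sentence names efficacy for both classes. Against the figures in step 3, it does not mention the consequence of higher exposure for the class that raises it.

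**5. Availability of data.** Appendix D says that there are no in vivo interaction data. Section 6.2 cites two drug-interaction trials, N=57 and N=22. Both statements cannot stand.

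**The case against.** The strongest reply is that nothing in Appendix D instructs a site to cut olaparib because of an inducer. The phrase covering both classes belongs to the exception step and not to the dosing sentence. The CRF reason and all three bullets say inhibitor, and inducers have a separate paragraph with no dose action. All 17 agents are prohibited whatever their label, criteria 3.2.7 and 3.2.8 separate the classes correctly at entry, and on-study use of a potent agent goes to case-by-case review. This largely stands. It makes an error unlikely, but it does not correct a list that labels nine drugs with the opposite class.

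On monitoring, section 7.2.1 records all adverse events, Appendix B schedules blood counts and chemistry every two weeks in Cycles 1-2 and monthly afterwards, and Appendix H manages olaparib toxicity. Watching efficacy after a dose cut is also reasonable. So toxicity is not left unobserved. The gap is confined to the interaction-specific sentence.

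A reader might go further and infer three things that the documents do not support.

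- That exposure is down 87% for any listed inducer. The figure is for rifampicin alone. Modafinil is classed as moderate, the only moderate-inducer figure is a simulation for efavirenz, and the other listed inducers have no figure.
- That a man on rifampicin would be left with about 4% of intended exposure (0.13 x 100/300 = 0.043). This needs the misreading to occur and pass review, and it needs dose proportionality, which 6.2 contradicts.
- That the trial loses power. If one of the 32 men could not succeed, the exact binomial chance of eight or more successes at a rate of 0.35 would fall from 0.918 to 0.899. But rifampicin already leaves only 13% of AUC at full dose, so any such loss would come mainly from the inducer. Rewording the appendix would not restore it.

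**Conclusion.** The point holds as a minor inconsistency in operative text on dosing and monitoring. Four defects stand: nine of 17 agents sit under the wrong class label; the dose-reduction sentence does not state its class, and the mislabelled list weakens the cues that would supply it; the interaction-specific monitoring sentence names only efficacy although 6.2 shows exposure moving in opposite directions; and the no-data statement contradicts 6.2. The finding is ambiguity, not an instruction to reduce olaparib for inducers. Few men are likely to be affected, since these drugs are prohibited and exceptions are reviewed individually. No effect on the trial's operating characteristics is claimed. The conclusion rests on the protocol's own drug classification and on the exposure figures in 6.2 as reported.

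**What to change.** In the next amendment, reconcile Appendix D with section 6.2 and criteria 3.2.7-3.2.8:

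- Correct the lead-in to the prohibited list so that the class of each agent matches the appendix's own classification and the eligibility criteria.
- State which class or classes the dose-reduction sentence covers, and make it agree with the CRF reason, the bullets and the inducer paragraph.
- Reconcile the monitoring sentence with the exposure data in 6.2 for each class.
- Replace the statement that no in vivo interaction data exist with a reference to 6.2.

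Which clinical rule applies to each class is for the sponsor to decide. No dose, monitoring rule or treatment action is proposed here. The cost is wording changes to about one page, with no added data or patients.
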